6.1.4 Kit number / Randomization number

The kit number, a unique randomization number will be assigned to each eligible subject at baseline according to the Inclusion/Non-inclusion criteria. Kit and randomization numbers will be allocated to each subject by the IRT system which will need to be accessed by the designated study site personnel in order to provide the intended kits.

6.1.5 Instructions for use and administration

All subjects randomized

The percentage of the body surface affected by the disease (BSA) will be estimated using the rule of nine's by the investigator and will be documented on the CRF and communicated to the subject.

Except for the first application, study drug will be applied at home by the subject on all the AD lesions (except scalp and genitals) as a thin layer corresponding to approximately 2 mg/cm^2 ([Shah 1992](#)) using the Finger Tip Unit (FTU). A finger-tip unit is the amount of ointment expressed from a tube with a 5 mm diameter nozzle applied from the distal skin-crease to the tip of the index finger ([Long 1991](#)). A member of the staff will instruct the subject on how to measure the prescribed dose using fingertip units (FTU): two FTUs are about the same as 1g of topical product.

Subjects will be instructed by the person in charge of dispensing study products, on the importance of being compliant with the daily applications, and the weekly visits on site. Please also refer to section [6.4](#) for the rules regarding dose modifications.

All explanations and training materials will be provided to the study centers before initiation of the study.

Applications should be made every evening approximately at the same time, preferably after showering. The subjects will be asked to complete a diary on a daily basis to record the products applications. Do not wash off within 2 hours after applications (hands included).

Additionally, in order to monitor the quantity of study product that has been applied by the subject during the previous week, the subject will have to return all used & unused tubes (i.e. the kit of the previous week) to the study centre during the planned study visits. Tubes will be weighed and the application procedures will be reminded to the subject so that the required quantity of products is applied, in compliance with the BSA.

All subjects will have to use their own emollient throughout the study duration once a day in the morning, including during the screening period.

Subjects dedicated to cutaneous procedures

The estimated time (HH:mm) when application of Day 42 is performed should be recorded by the subject and reported by a study staff member in the eCRF. The time of performance of the cutaneous procedures will be recorded by the study team at Day 43. A time-window of $12h \pm 2h$ should apply between the last product application and the cutaneous procedures.

6.1.6 Other supplies

Not Applicable.

CCI

CCI

6.4 Dose modification

In case the study treatment needs to be discontinued for any reason, as far as possible and if the subject agrees (see below) he/she should be followed as planned until the end of the clinical trial (also refer to section 5.4)

6.4.1 Tolerance issues

In case of significant sign and/or symptom of intolerance reported by the subject or assessed by the investigator, applications may temporarily be discontinued to allow the irritation to subside (treatment application could be performed every other day according to the Investigator judgement). The investigator should attempt to resume the daily applications as soon as possible, with respect to the local tolerance. This should be documented in the CRF and reported as an AE.

6.4.2 Decrease BSA

In case of improvement of the disease (*i.e.* a BSA decrease), the dose should remain unchanged throughout the study period, and subject will be asked to apply on all affected areas, even if they cleared.

Of note, the BSA should reflect the actual percentage of the zones affected by the disease; the previously affected areas that have cleared should no longer be taken into consideration for the calculation of this new BSA, even if they are still receiving the IMP.

6.4.3 Increase in BSA

In case of an increase in the BSA such as emergence of new plaques or extent of the surface of the identified ones, and within the limit of 8% (equivalent to 4g/day), the quantity of product to be applied will be recalculated during the study visit.

In case the BSA decreases afterwards, the rules of section [6.4.2](#) apply: the updated quantity that was calculated further to BSA increase will continue to be applied.

Should the BSA change because new plaques arise and former ones clear, the adjustment of the quantity of IMP should take into account the fact the applications should be maintained on the cleared zones. The BSA will be re-calculated, and the applications may be stopped on the oldest previously affected areas, to focus on the latest zones that have cleared, up to a maximum of 8%. The subject should be instructed not to use more than 4 gr/day (*i.e.* 8 FTUs). In case of flare (s)he should come back for an unscheduled visit.

Should the BSA increase above 8%, the investigator is to define whether treatment discontinuation and a rescue therapy is needed or not and whether the aggravation of the disease should be recorded as an AE. The investigator may also decide to maintain the products application, within a maximum amount corresponding to 8 FTUs/day (4g/day). **Should the treatment be discontinued, all efforts should be made for the subject to remain in the study until completion of study visits (see treatment discontinuation).**"

6.5 Blinding

6.5.1 Verification of blinding

This is an investigator-blind study. Test products are applied by the subject himself and the dispensation is done by a person who will not be involved in the assessment/evaluations. The investigator and/or other evaluator(s) will not come into contact with the study materials. The subject and members of the study staff do not have access to the correspondence between the kit number and the assigned treatment group.

6.5.2 Un-blinding during the clinical trial

Emergency un-blinding during the clinical trial may be required for therapeutic or for regulatory reasons (for expedited safety reporting).

A blind-break system will be available for Investigators. At the clinical trial center, use of an IRT system containing the identification of the assigned study drug(s) will be revealed in emergency situations only. In such an emergency, the Investigator will only break the blind for the subject involved.

The Investigator must notify the Sponsor's CSO immediately in the event of such an emergency (see contact details in Section [7.2.6.2.2](#)). If possible, the Investigator should notify the Sponsor before breaking the blind in order to discuss this decision with the Sponsor. The Investigator is required to document each case of emergency un-blinding on the appropriate form (provided by the Sponsor) and fax the completed form to the CSO immediately.

Bioanalytical and PD local un-blinding:

Sample assay for PK analysis (blood and skin) will only be performed on samples from subjects treated with CD5024. Prior to sample assay, local un-blinding will be performed (based on the randomization list transferred directly by the assigned representative of the clinical packaging organization), restricted to the Bioanalytical study director and his/her direct collaborators, in order to select the appropriate samples for the assay. Unblinded (SIN Number) bioanalytical results will only be disclosed after database lock, following a formal authorization provided by the Clinical Project Manager.

The same way, a list will be also transmitted to the Molecular Dermatology Unit study director, in charge of the PD analysis. Molecular dermatology results will only be disclosed, after database lock, following a formal authorization provided by the Clinical Project Manager.

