3 OVERALL CLINICAL TRIAL DESCRIPTION

This is an exploratory, multi-centric (approximately 5 sites in Canada), randomized, vehicle-controlled, investigator-blind, parallel group study, involving approximately 85 subjects screened to get approximately 60 randomized subjects with chronic lesions of AD meeting specific inclusion/non-inclusion criteria. The investigator and/or other evaluator(s) will not come into contact with the study materials. The subject and members of the study staff do not have access to the correspondence between the kit number and the assigned treatment group.

Subjects who consent to be enrolled and fulfil study criteria will be allocated to one of the study treatment according to the randomization list, in a 1:1 ratio (for example Group A: N=30 subjects treated by CD5024 0.3% cream and Group B: N=30 subjects treated by the vehicle). All subjects will undergo:

- a screening period ranging from 30 days to 3 days prior to Day 1
- a 6-week treatment period during which all plaques of AD (up to 8% BSA) will receive, depending on the randomization, either CD5024 0.3% cream or its vehicle once daily, for a total of 42 applications.
- a follow-up period of approximately 2 weeks after the last treatment applications.

CCI

Additionally, CCI and CCI assessments will be conducted on a subset of 20 subjects having received either CD5024 0.3% cream or its vehicle (10 subjects each) for 6 weeks. Tape-strips, D-squames and biopsies will be used to sample the appropriate skin material

needed for these assessments. Consequently, each subject having consented to have the procedures will undergo 3 biopsies (4-mm diameter) and have 20 tape-strips and 10 D-squames.

Except for the first day of application, all the applications will be made at home by the subjects at approximately the same time in the evening. All subjects will have to use their own emollient throughout the study duration once a day in the morning on AD lesions, including during the screening period. For those subjects who do not have an emollient, they will be prescribed one. Visits to the study center are planned every week to assess both safety and efficacy and to provide subjects with study treatments for the coming week. A total of 9 visits on site are planned.

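### The PD laboratory appears to receive treatment allocation before assay, and the one reason given for local un-blinding does not visibly apply to PD

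*Protocol*

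**What the plan says.** Protocol section 6.5.2 has a subsection headed "Bioanalytical and PD local un-blinding" that deals with two laboratories.

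For PK it sets out a full procedure:
- **Scope:** "Sample assay for PK analysis (blood and skin) will only be performed on samples from subjects treated with CD5024".
- **Timing:** "Prior to sample assay, local un-blinding will be performed".
- **Source of the information:** "based on the randomization list transferred directly by the assigned representative of the clinical packaging organization".
- **Purpose:** "in order to select the appropriate samples for the assay".
- **Access:** limited to the bioanalytical study director and immediate collaborators.
- **Release:** results are withheld until after database lock and need formal authorisation.

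For PD the text is much shorter. It likens the step to the PK one and says that "a list will be also transmitted to the Molecular Dermatology Unit study director, in charge of the PD analysis". It then adds one safeguard: "Molecular dermatology results will only be disclosed, after database lock, following a formal authorization provided by the Clinical Project Manager". It does not state what the list contains, when it is sent, why it is needed or who else in the unit may see it.

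Section 3 (and the synopsis, under trial design) defines the group that has skin procedures as a "subset of 20 subjects having received either CD5024 0.3% cream or its vehicle (10 subjects each) for 6 weeks". Each consenting subject, in either arm, has 3 biopsies, 20 tape-strips and 10 D-squames.

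**The concern.** Local un-blinding of a laboratory is acceptable where the assay itself requires it. The PK assay does, since the laboratory cannot measure only active-arm samples without knowing which they are. The protocol then carries the same arrangement over to a unit whose material comes from a subset with both arms equally represented, and gives no separate reason for doing so.

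If the PD unit knows the arm while it works, that knowledge can affect choices made at the bench: how samples are batched, which are rejected or repeated, and how anything graded by eye is read. The release rule does not address this. It stops PD results from reaching the clinical team early, whereas the exposure here runs the other way, from treatment allocation into the PD results.

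What is at stake is the credibility of the skin data from 20 of about 60 randomised subjects in what section 1.1 presents as a proof-of-concept study. The material is obtained invasively: the 10 vehicle subjects alone contribute 10 × 3 = 30 biopsies.

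**Working it through.** The point concerns blinding and contains no figure of the plan to reproduce. The check is to set the statements side by side.

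**Step 1. Does the PD unit receive allocation, and when?** The PD sentence speaks only of a list. Three features of section 6.5.2 indicate its nature:
- the heading names PD together with bioanalysis as un-blinded;
- the sentence opens by likening the step to the PK procedure;
- it says the list is also transmitted, following a paragraph in which the randomization list is what is transmitted.

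The natural reading is a list with treatment allocation, available before assay. This is an inference. The document states content and timing for PK only.

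**Step 2. Does the stated reason carry over?**

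| | PK | PD |
|---|---|---|
| Arms assayed | CD5024 only (6.5.2) | Not stated in visible text |
| Arms sampled in the skin subset | Both, 10 and 10 (section 3) | Both, 10 and 10 (section 3) |
| Reason for the list | Selecting samples for assay (6.5.2) | None stated |
| Timing of the list | Before assay (6.5.2) | Not stated; inferred from the PK text |
| Access limit | Study director and immediate collaborators (6.5.2) | None stated beyond the addressee |

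Section 6.5.2 excludes vehicle samples from the PK assay of blood and skin. The visible research use that remains for the vehicle subjects' skin samples is the PD or molecular work. If those samples are assayed, there is no active-only set to pick out, and the PK reason does not apply.

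**Step 3. Does the stated safeguard cover the gap?** Section 6.5.1 keeps the treatment key from the investigator, other evaluators, subjects and study staff. Section 6.5.2 holds PD results back until database lock. Together these protect EASI, IGA and the safety assessments. Neither protects PD assay, exclusion or reading decisions from knowledge of the arm, and section 6.5.2 names no coding of PD samples.

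**Step 4. Size.** No assay type, PD endpoint or PD test is visible, so the bias cannot be computed. As a matter of scale only, one sample handled differently is 1/10 = 10% of an arm in the subset and two are 2/10 = 20%. These are hypothetical counts; nothing in the document says that any sample would be excluded or repeated.

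**The case against.** The strongest reply is that much of the PD plan is redacted: an objective, the names of the subset assessments, and blocks of the assessment and statistical sections. A reason for the list, a coding scheme or a rule for blinded reading could stand there. Section 8.1.5 also refers the skin procedures to an operational manual that is not at hand. This stands. A reader might infer that the PD laboratory is un-blinded without any need; the documents do not support that, because redacted text cannot be counted as absent. They support only that the one visible reason does not visibly apply.

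A reader might also infer that PD samples of both arms must be assayed and compared. That is likely, given 10 subjects per arm, but no visible passage states a between-arm PD comparison, its endpoint or its test.

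There may also be a practical use for allocation. The skin procedures depend on consent, and no stratification of the subset by arm is visible, so reaching 10 and 10 could require someone to know the arm. Skin material might also have to be routed by arm for the PK assay. The document gives neither as its reason, and both could be handled by a party outside the PD unit, so this shapes the fix without removing the point.

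Finally, the harm is not demonstrated. Purely instrument-read assays would be less exposed than graded readings, and the visible text does not say which are used. The trial describes itself as exploratory, and the main efficacy and safety assessments remain blind. These arguments limit the severity. They do not supply a reason for the visible sentence.

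**Conclusion.** The point holds in a limited form, at low severity. Section 6.5.2 places the head of the PD analysis under a local un-blinding arrangement whose only stated purpose, selecting CD5024 samples for PK, does not visibly fit PD. The disclosure rule does not keep the PD work itself blind.

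This rests on two assumptions: that the PD list carries allocation and is available before assay, as the heading and wording indicate, and that no redacted text provides a reason or a blinded procedure. If either fails, what remains is a sentence that should state its purpose, content and timing.

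The possible bias is confined to the PD data of the 20-subject subset, and its size cannot be stated. The primary EASI analysis, the secondary efficacy endpoints and the safety conclusions are unaffected.

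**What to change.** Rewrite the PD sentence in section 6.5.2 to say that:
- the PD unit works on coded samples without treatment identity;
- its results file is finalised and locked;
- treatment codes are merged only after database lock.

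If samples must be selected or batched by arm, the packaging organisation, which already holds the randomization list, supplies a coded sample list or run order that does not reveal treatment. Local un-blinding of the PK laboratory stays as written.

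The cost is one amended paragraph, a matching line in the laboratory manual and minor logistics for coding the samples. No subjects, samples or assays are added, and sample size, power and type I error do not change.

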7 CLINICAL TRIAL ASSESSMENT

7.1 Efficacy assessments

7.1.1 Investigator Global Assessment (IGA)

IGA should be a global static evaluation of the severity of the disease. A 5-point IGA (ranging from 0 to 4) will be performed by the investigator at screening and on Day 1, Day 8, Day 15, Day 22, Day 29, Day 36 and Day 43 or earlier in case of early termination. IGA (whole body assessment) should be equal to 3 at Day 1.

Table 5 IGA

Status	Score	Definition
Clear	0	Minor, residual discoloration, no erythema or induration/papulation, no oozing/crusting.
Almost clear	1	Trace, faint pink erythema with almost no induration/papulation and no oozing/crusting.
Mild	2	Faint pink erythema with mild induration/papulation and no oozing/crusting.
Moderate	3	Pink-red erythema with moderate induration/papulation and there may be some oozing/crusting.
Severe	4	Deep/ bright red erythema with severe induration/papulation with oozing/crusting.

7.1.2 Hand IGA

If the subject presents with atopic dermatitis on one or both hands at baseline, the investigator will also assess the severity of the hand eczema from 0 to 4 (0:clear, 1:almost, 2:mild, 3:moderate, 4: severe) at Day 1, Day 8, Day 15, Day 22, Day 29, Day 36 and Day 43 or earlier in case of early termination.

7.1.3 BSA

The BSA is the percentage of the total body surface area (tBSA) affected by atopic dermatitis, presenting with some, or all, of the individual features of the disease. It can evolve throughout the study duration. It should reflect the actual percentage of the body surface (except scalp and genitals) area affected by the disease; the previously affected areas that have cleared should no longer be taken into consideration for the calculation of the new BSA, even if they are still applied the IMP, as discussed in section 6.4.

The BSA, determined using the Rule of Nine's, is a good indicator of the disease's state and will also be used for the calculation of the modified objective SCORAD. The BSA will be assessed

at screening, at Day 1, Day 8, Day 15, Day 22, Day 29, Day 36 and Day 43 or earlier in case of early termination and at the unscheduled visit if applicable.

Of note, at Day 1, BSA should comprise between 1% inclusive and 10% inclusive (excluding scalp and genitals).

tBSA is the subject's surface of the body, expressed in square meter. Several publications deal with the way to calculate tBSA. The mosteller formula is however recommended for use in this protocol: $BSA (m^2) = \text{SQRT}([Height(cm) \times Weight(kg)]/3600)$ or in inches and pounds: $BSA (m^2) = \text{SQRT}([Height(in) \times Weight(lbs)]/ 3131)$ ([Mosteller 1987](#)).

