1.3 Risk/Benefit assessment

The proposed clinical study intends to evaluate the safety and efficacy of CD5024 cream 0.3% in patients with AD and the preclinical and clinical data supporting the positive benefit risk ratio in this particular study are detailed below.

CCI

In the present study a formulation with a lower concentration of CD5024 (0.3%), will be used to take into account a larger BSA of application (up to 8% in the study). An average of 3.4 g of a formulation at 0.3% (containing 10.2 mg of CD5024 which is similar to the dose applied for

rosacea) and a maximum of 4g of formulation (containing 12 mg of CD5024 corresponding to approximately 200 µg/kg body weight) will be applied during the study on subjects with AD. As AD lesions may be characterized by skin barrier impairment, the transdermal absorption might be higher in those subjects in comparison to PPR subjects and therefore a somehow higher systemic exposure is expected than in PPR subjects.

It should be also taken into account that, in addition to these high safety margins after topical exposure, CD5024 has also been used by the oral or subcutaneous routes in humans at doses ranging from 200 to 2000 µg/kg body weight during periods up to 12 weeks and was generally well tolerated (see section 1.3.2). Given the lower relative bioavailability of topical CD5024 compared to the oral or subcutaneous administration, the systemic exposure in the present study is expected to remain lower than the exposure seen in these trials.

With regards to pregnant women, given the animal teratogenicity data and in absence of well controlled data on safety in pregnant women, contraceptive methods will be mandatory for females of childbearing potential.

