5.2.1 Inclusion criteria

1. The subject is a male or female aged 18 to 60 years old inclusive at Screening;
2. The subject presents with a tBSA $\leq 2.5 \text{ m}^2$ at Screening;
3. The subject is a female of childbearing potential who agrees to use a highly effective and approved contraceptive method for the duration of the study defined as:
 - 3.1. bilateral tubal ligation OR,
 - 3.2. combined oral contraceptives (estrogens and progesterone), implanted or injectable contraceptives on a stable dose for at least 1 month prior to Day 1 OR,
 - 3.3. hormonal intra-uterine device (IUD) inserted at least 1 month prior to Day 1 OR,
 - 3.4. vasectomized partner for at least 3 months prior to Day 1 and this male is the sole partner for that subject;
4. If the subject is a female of childbearing potential, she has a negative UPT at Screening & Day 1 visits
5. The subject is a female of non-childbearing potential, defined as postmenopausal (absence of menstrual bleeding for 1 year prior to screening, without any other medical reason), or had a hysterectomy or a bilateral oophorectomy;
6. The subject has atopic dermatitis for at least 6 months prior to Day 1. The clinical diagnosis of atopic dermatitis must be confirmed with the criteria of Hanifin and Rajka at the screening visit;
7. Atopic dermatitis must be stable for at least one month before the screening visit (according to subject);
8. The subject has a Body Surface Area (BSA) affected by AD ranging from 1% inclusive to 8% inclusive at Day 1, excluding scalp and genitals;
9. The subject has an AD with an overall Investigator's Global Assessment (IGA) score of 3 (moderate) at Day 1;
10. The subject is willing and able to comply with all of the time commitments and procedural requirements of the clinical trial protocol;
11. The subject has understood and signed an Informed Consent Form (ICF) at screening, prior to any investigational procedures being performed;

12. The subject is apprised of the Personal Information Protection and Electronic Documents Act (PIPEDA) and is willing to share personal information and data, as verified by signing a written authorization.

Rationale:

#1; 3 to 5: Given the animal teratogenicity data and in absence of well controlled data on safety in pregnant women, contraceptive methods will be mandatory for females of childbearing potential.

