9.1.2 Populations analyzed and evaluability

The statistical analyses will be performed based on the following subject populations:

9.1.2.1 *Intent-to-treat (ITT) Efficacy analysis set*

The ITT set is defined as any subjects who are randomized. Data from subjects included in the ITT population will be analyzed according to the treatment as randomized.

9.1.2.2 *Per-protocol (PP) Efficacy analysis set*

Per Protocol (PP) set is defined as the ITT population, after exclusion of subjects deemed non-evaluable for efficacy due to major deviations from the protocol. Major deviations are categorized into 4 categories:

- Entrance criteria deviations,
- Non compliance,
- Concomitant therapies taken during the study and/or Concomitant illnesses, interfering with efficacy,
- Administrative errors such as unblinding or study drug dispensing errors.

Major deviations will be identified and categorized before database lock and unblinding, during a blind data review meeting.

9.1.2.3 *Safety Analysis set*

The Safety set is defined as comprising the ITT Population subjects who applied/were administered the study drug(s) at least once. In practice, only the subjects who return their study drug(s) unopened will be excluded from the Safety Population. All safety data will be summarized based on the Safety Population.

9.1.3 *Data presentation and graphics*

For statistical analyses purpose, baseline is defined as the last measurement prior to the first application of the study drug.

A type I error of 0.05 (two-sided test) will be used to declare statistical significance.

The subject disposition, demographics, Baseline characteristics, previous therapies/procedures, concomitant therapies/procedures will be summarized by descriptive statistics based on the ITT population. Treatment duration and compliance data will be summarized based on the Safety Population.

For statistical analysis purposes, previous therapies/procedures are defined as those ending at Baseline or before; and concomitant therapies/procedures are defined as those ongoing at the Baseline visit or starting after the Baseline visit.

All efficacy variables will be summarized by treatment at each visit. The categorical variables (e.g. IGA), and their changes from Baseline will be summarized by frequency and percentage for each response category (N, %). The continuous variables (EASI, objective SCORAD, TSS, and their percent changes, Pruritus (weekly average NRS), VRS and their changes from baseline)

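### Section 7.1.3 allows affected BSA up to 10% at Day 1, but inclusion criterion 8 and the 4 g/day cap are set at 8%

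*Protocol*

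**What the plan says.** Section 7.1.3 (BSA) closes its account of the assessment with a Day 1 range: "Of note, at Day 1, BSA should comprise between 1% inclusive and 10% inclusive (excluding scalp and genitals".

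Inclusion criterion 8 in section 5.2.1 reads: "The subject has a Body Surface Area (BSA) affected by AD ranging from 1% inclusive to 8% inclusive at Day 1, excluding scalp and genitals". The synopsis repeats this criterion with the same limit.

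The other sections that depend on the limit also use 8%:

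- Section 3 (design): "a 6-week treatment period during which all plaques of AD (up to 8% BSA) will receive" active cream or vehicle.
- Section 1.3 (risk/benefit) explains the lower 0.3% strength as chosen "to take into account a larger BSA of application (up to 8% in the study").
- Section 6.4.3 equates the 8% limit with 4 g/day and adds: "The subject should be instructed not to use more than 4 gr/day", which it gives as 8 fingertip units. It treats a rise above 8% during the study as a prompt to consider stopping treatment and giving rescue therapy.

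Section 6.1.5 sets a layer of about 2 mg/cm² and states that "study drug will be applied at home by the subject on all the AD lesions (except scalp and genitals"). Inclusion criterion 2 limits total body surface area (tBSA) to 2.5 m².

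**The concern.** Two sections give different upper limits for the same quantity at the same visit. The lower bound (1%) and the excluded sites are identical, so the sentence in 7.1.3 can only be a restatement of criterion 8 with a different number. Section 7.1.1 restates criterion 9 in the same way, requiring an IGA of 3 at Day 1, and there the figures agree.

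The wrong figure sits in the section a site consults when it scores BSA. The baseline visit list in section 8.1.2 puts the eligibility check at step 7, the BSA assessment at step 8 and randomisation at step 13. If a site follows that order, Day 1 BSA is scored after eligibility has been confirmed, and 7.1.3 is then the text at hand.

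A subject entered with more than 8% and up to 10% would:

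- breach criterion 8 and fall under "Entrance criteria deviations", one of the four categories of major deviation for the per-protocol set (section 9.1.2.2), while remaining in the ITT set;
- be above the treatment limit from the first application;
- meet two instructions that no longer agree: treat all lesions (section 6.1.5), or treat plaques up to 8% BSA (section 3).

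EASI, the primary efficacy endpoint, scores all four body regions, so any under-treated lesion would count in it.

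**Working it through.** **Inputs**

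- Layer: about 2 mg/cm² (section 6.1.5).
- Maximum tBSA: 2.5 m² = 25,000 cm² (criterion 2).
- Daily cap: 4 g = 4,000 mg (section 6.4.3).
- Competing Day 1 limits: 8% (criterion 8) and 10% (section 7.1.3).

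**Reproducing the cap**

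Amount needed = BSA share × tBSA in cm² × 2 mg/cm².

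- At 8%: 0.08 × 25,000 × 2 = 4,000 mg = 4.0 g, which is the stated cap.
- At 10%: 0.10 × 25,000 × 2 = 5,000 mg = 5.0 g, which is 25% above the cap.

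The cap therefore follows from 8% and not from 10%. The 5.0 g is what the target layer would need. The protocol does not permit it.

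**What the cap means above 8%**

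- tBSA at which 4 g is just enough = 4,000 / (2 × BSA share × 10,000) m².
- Layer at the cap with tBSA 2.5 m² = 4,000 / (BSA share × 25,000) mg/cm².
- Share of affected skin untreated if treatment is held to 8% = (BSA − 8) / BSA.

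| Day 1 BSA | Needed at 2.5 m² | tBSA at which 4 g just suffices | Layer at the cap, 2.5 m² | Untreated share if held to 8% |
|---|---|---|---|---|
| 8% | 4.0 g | 2.50 m² | 4,000/2,000 = 2.00 mg/cm² | 0 |
| 9% | 4.5 g | 2.22 m² | 4,000/2,250 = 1.78 mg/cm² (11% less) | 1/9 = 11% |
| 10% | 5.0 g | 2.00 m² | 4,000/2,500 = 1.60 mg/cm² (20% less) | 2/10 = 20% |

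For scale, the Mosteller formula that section 7.1.3 recommends gives √(180 × 80 / 3600) = 2.00 m² for a subject of 180 cm and 80 kg. At 10% BSA the cap therefore binds only in subjects larger than that.

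**Weight in the analysis**

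With 30 subjects per arm, each ineligible subject is 1/30 = 3.3% of an arm. The sample size calculation in section 9.2 does not use the BSA limit and is unaffected.

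**The case against.** The strongest reply is that section 7.1.3 does not decide eligibility. Section 5.2 requires every listed criterion to be met, section 6.1.4 assigns randomisation numbers according to those criteria, and section 8.1.2 requires them to be confirmed before randomisation. A site would have to put a side remark above the formal criterion. This stands as a reason to expect few cases. It does not remove the contradiction, and the step order in section 8.1.2 weakens the safeguard somewhat.

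Second, section 6.4.3 already accepts continued treatment above 8% under the 4 g cap, so a thinner layer in some subjects is foreseen. That is true for increases during the study. The section is not written for subjects who enter above the limit.

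Third, the 11% and 20% thinner layers require both a BSA above 8% and a tBSA at the 2.5 m² maximum, and the 2 mg/cm² layer is itself approximate and self-measured in fingertip units. The untreated-skin figures depend on reading section 3 as a limit on the treated area. Both sets of figures are worst cases. Any mistaken entry would precede randomisation, so it should not favour either arm; at most it would dilute the effect. Per-protocol exclusion is also not automatic, because it is decided at a blind review before database lock. All of this is accepted.

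Finally, the modified objective SCORAD range of 0 to 65 in section 7.1.5 fits 10% exactly: 10/5 + 7 × 18/2 = 65. But 8% gives 1.6 + 63 = 64.6, which rounds to 65, and BSA may rise during the study. The range says nothing about entry at Day 1.

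**Conclusion.** The contradiction is real, and 10% is the wrong figure. Criterion 8 governs entry, the other sections that state a limit use 8%, and 8% reproduces the 4 g cap exactly given a tBSA limit of 2.5 m² and a layer of 2 mg/cm².

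The consequence is avoidable eligibility deviations, not excess exposure. Under-treatment is bounded at 20%, in layer thickness or in coverage, for a subject at 10% BSA. The layer figure assumes the maximum tBSA; the coverage figure assumes that treatment is held to 8%. No effect on EASI or on power has been quantified, and the number of subjects cannot be known from the protocol. The point should be fixed because the wrong threshold is in an operative section and the correction is trivial.

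**What to change.** In section 7.1.3, change 10% to 8%, or replace the sentence with a reference to inclusion criterion 8 so that the limit is stated in one place. If the eCRF has an edit check on Day 1 BSA, confirm that it uses 8%; the protocol does not describe such a check, so this is a precaution.

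The 4 g (8 fingertip unit) cap, section 6.4.3 and the SCORAD range need no change. The cost is one wording correction and, where relevant, a look at the eCRF limit. No subjects, visits or procedures are added.
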